10.2. Safety Variables

Patients in the safety population will be included in safety analyses.

Adverse events will be coded using the Medical Dictionary for Regulatory Activities (MedDRA), and the severity of AEs and laboratory abnormalities will be graded using the NCI CTCAE, version 5.0 ([US DHHS 2017](#)). AEs will be tabulated by system organ class (SOC) and preferred term. Incidence tables of patients with AEs, SAEs, and DLTs will be presented by maximum severity.

Clinical laboratory data, ECGs, and other safety assessments will be presented in by-patient listings and will be presented in tabular format, including absolute values and changes from baseline (if applicable), by dose cohort, cycle, and study day.

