- Trial Day 1 of Cycle 1 is defined as the day on which the first dose of SYNB1891 is administered. Study days after trial day 1 will be calculated as the difference between the date of interest and the first date of dosing of study medication plus 1 day. The generalized calculation algorithm for relative day: STUDY DAY = [(TARGET DATE – DSTART) + 1 where DSTART = the start day of study drug].
- For dates of interest before the first date of dosing of study medication, the study day will be calculated as: STUDY DAY = TARGET DATE – DSTART. Negative study days are reflective of observations obtained

prior to first study drug administration. Note: Partial date for the first study drug is not imputed in general. All effort should be tried to avoid incomplete study drug start date.

- Age (years) at informed consent will be calculated as: (Date of informed consent – date of birth+1)/365.25 and then truncated to an integer. In case of partial birth date: impute missing day as 15th of the month; impute missing month as July; set missing age for missing year.
- Duration will be calculated by the difference of start and stop date + 1. AE duration (days) = AE end date – AE start date +1; study drug exposure duration (weeks) = (date of the last dose – date of the first dose + 1)/7.
- Time since disease diagnosis (months) will be calculated as (Informed Consent Date – Diagnosis Date +1)/ 30.4167.
- The time since an event will be calculated as date of event minus reference date. The specific censoring rules on the endpoint will follow section VII.
- The following conversion factors will be used to convert days to months or years:
 - 1 month = 30.4167 days
 - 1 week = 7 days
 - 1 year = 365.25 days
- Multiple Assessments for the Same Assessment Time Point

In the case of multiple observations (e.g. scheduled vs. unscheduled) at a specific visit, the first non-missing measurement will be used for analysis, unless multiple study assessments are expected (e.g., pre-dose vs post-dose). When multiple study assessments are expected, the first non-missing measurement for the visit and assessment time point will be used for analysis.

VI. Subject Accountability

A. Disposition

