DLT events will be included in the AE listings and the number and percentages of patients who experience DLT will be summarized. Detailed information about DLT is described in protocol section 4.2.4.

C. Adverse Events

Adverse events (AEs) will be documented on the AE eCRF and monitored continuously throughout the study. Adverse events will be coded using the Medical Dictionary for Regulatory Activities (MedDRA), version 22.0, associating lower-level terms with preferred terms and system organ classes by the primary hierarchy. All adverse events will be included in the listings.

Treatment Emergent Adverse Events (TEAE) are defined as any event that occurs or worsens on or after the day study treatment SYNB1891 is initiated through the safety follow-up visit (30 ± 5 days after the last dose of study treatment) except the SAEs related to the study treatment after safety follow-up. The tables will display counts and percentages of patients who reported at least one treatment-emergent

adverse events (TEAE) in each system organ class represented in the AE data. Within each system organ class, the tables will display the counts and percentages of patients reporting at least one TEAE, as designated by the preferred terms.

Adverse events of special interest (AESIs) (serious or nonserious) are a subset of pre-specified adverse events including 1) cytokine release syndrome, 2) grade 3 or higher systemic infection and 3) grade 3 or higher local injection site reactions. Detailed definition about adverse events of special interest for SYNB1891 can be found in protocol section 9.3.

The severity of adverse events will be graded using the NCI Common Toxicity Criteria for Adverse Events (CTCAE version 5.0). The intensity is assigned a grade of 1 through 5 using the following CTCAE guidelines: Grade 1 – Mild; Grade 2 – Moderate; Grade 3 – Severe; Grade 4 – Life-threatening; Grade 5 – Death.

The causality of AE will be classified as either related to study drug (possibly, probably, or definitely related) or not related to study drug (unlikely, probably not related, or definitely not related).

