- Serious TEAEs related to each study drug separately. This table will include Serious TEAEs with a drug relationship of “Definitely Related”, “Probably Related” or “Possibly Related”. It will also include Serious TEAEs with missing drug relationships. An SAE reported by a patient more than once will be included in this table if at least one of the drug relationship is one of the categories listed here.
- All Grade 3 or above TEAEs
- Grade 3 or above TEAEs related to each study drug separately. These tables will include Grade 3+ TEAEs with the same constraints as TEAEs related to study drug
- All TEAEs leading to discontinuation of study treatment (SYNB1891, atezolizumab, and overall)
- All TEAEs leading to dose interruptions (of SYNB1891 and atezolizumab separately)
- All TEAEs leading to dose modifications (of SYNB1891 and atezolizumab separately)
- All TEAEs leading to death
- TEAEs of special interest (AESIs)

c. All AEs by System Organ Class, Preferred Term and CTCAE toxicity grade

d. All AEs by System Organ Class, Preferred Term and action taken with each drug separately (SYNB1891 and atezolizumab)

e. A separate summary of AEs by Preferred Term for all AEs will be provided.

The following AE listings (including all AEs - TEAEs and non-TEAEs) will be produced (sorted by dose cohort, patient, and time):

- All AEs
- All SAEs
- AESIs
- AEs leading to discontinuation of study treatment

- AEs leading to death

D. Clinical Laboratory Results

Clinical laboratory tests will be performed (predose unless otherwise specified) at the timepoints indicated in Appendix 3. Baseline laboratory measurements do not need to be repeated if screening measurements were performed within 3 days prior to Cycle 1 Day 1. Local laboratories may review all hematology, chemistry, thyroid function, coagulation and urinalysis. Central laboratories will review all cytokines, qPCR and tumor samples collected for exploratory analysis. All laboratory data will be converted to standardized conventional units for reporting purposes. Appendix 4 outlines the clinical laboratory measurements that will be reviewed at the local and central laboratory.

E. Vital Signs

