Vital signs (systolic blood pressure, diastolic blood pressure, body temperature, pulse, and pulse oximetry) will be summarized with continuous descriptive statistics at screening, on Cycle 1 Day 1 (predose and 30 minutes, 1 hour, 2 hours, 3 hours, 6 hours, and 24 hours postdose), on all study treatment days (predose and 30 minutes, 1 hour, 2 hours, 3 hours, and 6 hours postdose), at EOT/Early Termination and Safety Follow up.

F. Physical Examination

Complete physical examinations will be performed at screening and Baseline, with symptom-directed physical examinations performed at subsequent time points (see Appendix 3). As a part of the physical examination and prior to each dose, a photograph of the visible injected and/or noninjected lesion(s) should be taken at the discretion of the Investigator. No information from the photo will be included into the analysis. A listing of patients' Physical Examination completion status will be provided.

G. Electrocardiograms

Semi-supine single 12-lead ECGs will be performed at screening and reviewed locally. An overall interpretation of the ECG results will be made and QT, corrected by Fridericia's formula (QTcF), intervals will be listed.

H. Multi-gated Acquisition Scan or Echocardiogram

MUGA or ECHO will be performed within 6 months prior to the first dose of study treatment provided the patient has not received any potential cardiotoxic agents in the intervening period. If potential cardiotoxic agents have been administered within 6 months, patients must undergo a MUGA/ECHO during the

screening period. Left Ventricular Ejection Fraction and an overall interpretation will be listed.

Assessments performed at screening visit, Virology (hepatitis B, C and HIV), ECGs, MUGA/ECHO, Urinalysis will be listed by patient. Clinical laboratory results, vital sign and Physical examination will be listed by patient and summarized by Arm, dose and visit in the Safety population. Summaries of baseline values and changes from baseline will be presented by dose level for each assessment time point. Shift tables summarizing the counts and percentages of patients who were normal at baseline, but who became abnormal subsequently, will also be displayed.

IX. Pharmacodynamics and Pharmacokinetics

PK and PD analysis may be reported in a separate report.

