37	Incidence of Treatment Emergent Adverse Events Resulting in SYNB1891 Dose Modification by System Organ Class and Preferred Term, Number (%) of Patients	Safety	
38	Incidence of Treatment Emergent Adverse Events Resulting in Atezolizumab Dose Modification by System Organ Class and Preferred Term, Number (%) of Patients	Safety	
39	Incidence of Treatment Emergent Adverse Events Resulting in Death by System Organ Class and Preferred Term, Number (%) of Patients	Safety	
40	Incidence of Treatment Emergent Adverse Events of Special Interest by System Organ Class and Preferred Term, Number (%) of Patients	Safety	E1
41	Incidence of Treatment Emergent Adverse Events by System Organ Class, Preferred Term and Maximum Severity, Number (%) of Patients	Safety	E1
42	Incidence of Treatment Emergent Adverse Events by System Organ Class, Preferred Term and Action Taken, Number (%) of Patients	Safety	
43	Incidence of Treatment Emergent Adverse Events by Preferred Term, Number (%) of Patients	Safety	
44	Mean Change in Clinical Chemistry Parameters Over Time	Safety	
45	Mean Change in Hematology and Coagulation Parameters Over Time	Safety	
46	Mean Change in Thyroid Function Parameters Over Time	Safety	
47	Mean Change in Vital Signs Over Time	Safety	
48	Mean Change in Pharmacodynamic Over Time	PK/PD	
49	Mean Change in Pharmacokinetics Over Time	PK/PD	

	Listing Title	Analysis Population	Interim Analysis (1st at the end of Arm 1 Cohort 4 [C4]; 2nd at the end of Arm 1 [E1]; or both [X])	Comment
1	Patient Disposition	Safety	X	
2	Screening and Enrollment Status	Safety	X	
3	Protocol Deviations	Safety	X	
4	Demographic Characteristics	Safety		
5	Subject Medical History	Safety		
6	Disease History	Safety	X	
7	Prior Anti-Cancer Systemic Therapy	Safety	X	
8	Prior Anti-Cancer Radiotherapy	Safety		
9	Prior/Concomitant Medications	Safety		
10	Prior/Concomitant Procedures	Safety		
11	Intratumoral Administration of SYNB1891	Safety	X	
12	Administration of Atezolizumab by IV Infusion	Safety		
13	Dosing Compliance/Exposure	Safety		
14	Core Biopsy of Lesion	Safety		
15	RECIST 1.1 Target Lesions	Safety	E1	
16	RECIST 1.1 Non-Target Lesions	Safety	E1	
17	RECIST 1.1 New Lesions	Safety	E1	
18	RECIST 1.1 Injected Lesions	Safety	E1	
19	RECIST 1.1 Response Assessment	Safety	X	19.1. iRECIST
20	LYRIC Target Lesions	Safety	E1	
21	LYRIC Non-Target Lesions	Safety	E1	
22	LYRIC New Lesions	Safety	E1	
23	LYRIC Injected Lesions	Safety	E1	
24	LYRIC Response Assessment	Safety	X	
25	Adverse Events	Safety	X	

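### The SAP's shift tables count only normal-to-abnormal changes, so worsening from an abnormal baseline is missing from the categorical laboratory summary, and no CTCAE-graded laboratory summary is specified

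*SAP*

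**What the plan says.** The closing paragraph of SAP VIII.H sets out three kinds of laboratory display. First, "Clinical laboratory results, vital sign and Physical examination will be listed by patient and summarized by Arm, dose and visit in the Safety population". Second, "Summaries of baseline values and changes from baseline will be presented by dose level for each assessment time point". Third, "Shift tables summarizing the counts and percentages of patients who were normal at baseline, but who became abnormal subsequently, will also be displayed". The third is the only categorical laboratory summary in the SAP text.

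Protocol 10.2 states that "the severity of AEs and laboratory abnormalities will be graded using the NCI CTCAE, version 5.0". SAP VIII.C applies CTCAE version 5.0 to adverse events and does not mention laboratory values. SAP VIII.D, on laboratory results, gives one data-handling rule, on units: "All laboratory data will be converted to standardized conventional units for reporting purposes".

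For several observations at one visit, including a scheduled and an unscheduled one, SAP V.F says that "the first non-missing measurement will be used for analysis".

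For chemistry, hematology, coagulation and thyroid data, Appendix 5 of the SAP lists mean-change tables (Tables 44 to 46; Table 44 is "Mean Change in Clinical Chemistry Parameters Over Time") and plain listings (Listings 30 to 32). It lists neither a laboratory table by grade nor the shift tables promised in VIII.H.

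**The concern.** A shift table shows how many patients got worse on a test, and from what starting point. This one has a single starting point, normal. In advanced cancer, with eligibility limits set at multiples of the ULN, some patients will start elsewhere. For them the table records nothing, whether the value stays put or rises several-fold.

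The stake is the safety description by dose. The trial is first-in-human, liver lesions may be injected (Protocol 5.2.1.1), and immune-mediated hepatitis is a stated atezolizumab risk (Protocol 4.4.2.2). Liver tests are therefore where a count of patients who worsened, and to what grade, is most useful. They are also where eligibility most clearly admits abnormal baselines.

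**Working it through.** The documents give no figure on this point, so the check is mainly a comparison of text.

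**1. Who can be abnormal at baseline.** Protocol 5.2.1.1 admits:
- AST, ALT and alkaline phosphatase up to 2.5 × ULN; AST and ALT up to 5 × ULN with liver metastases; alkaline phosphatase up to 5 × ULN with liver or bone metastases.
- Total bilirubin up to 1.5 × ULN, and higher under stated conditions.
- INR, PT or aPTT up to 1.5 × ULN, with an allowance for patients on anticoagulants.
- Hemoglobin from 9.0 g/dL, with transfusion allowed. Whether this is abnormal depends on the local reference range, which the documents do not give.

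A value above the ULN is abnormal by definition, so these patients fall outside the shift table for that test. They still count for every test on which they start normal.

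**2. Where worsening from an abnormal baseline would appear.**

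| Display | Includes the patient? | Gives a count by grade and dose? |
|---|---|---|
| Shift table (VIII.H) | No | No |
| By-patient listings, including unscheduled assessments (Listing 43) | Yes | No |
| Change-from-baseline summaries, Tables 44 to 46 | Yes, averaged | No |
| AE tables by CTCAE grade (VIII.C) | Only if recorded as an AE | Yes |

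The AE route depends on Protocol 7.2.5 and 9.6: clinical significance, a dosing action, an intervention, or Investigator discretion.

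**3. An example that can miss the AE route.** Take a patient with liver metastases whose ALT goes from 2 × ULN to 5 × ULN, a rise of 5 / 2 = 2.5-fold. Protocol 7.2.5.1 requires the eligibility limits to be met on dosing days, and 5 × ULN still meets the limit. That check alone triggers no dosing action. Recording as an AE then turns on the other conditions. The shift table counts zero. If the other patients do not change, the mean change is (5 − 2) / 3 = 1 × ULN in a 3-patient cohort and (5 − 2) / 20 = 0.15 × ULN in a 20-patient group. Neither mean shows that one patient moved.

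**4. How many patients.** Let q be the share abnormal at baseline on a given test. The documents do not give it; 10% to 60% is assumed. Cohorts start at 3 patients, and up to 20 may be added at the recommended Phase 2 dose (Protocol 4.2.3). The chance that a 3-patient cohort has at least one patient who cannot be counted is 1 − (1 − q)³. The expected number in 20 is 20q.

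| q | 1 − (1 − q)³ | 20q |
|---|---|---|
| 10% | 1 − 0.729 = 27% | 2 |
| 20% | 1 − 0.512 = 49% | 4 |
| 40% | 1 − 0.216 = 78% | 8 |
| 60% | 1 − 0.064 = 94% | 12 |

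**5. The value that is selected.** The first-value rule keeps the worse of two values only when the worse one comes first. The SAP defines no worst post-baseline laboratory value, so a later, worse result at the same visit can drop out of the summaries, though not out of the listings.

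**The case against.** The strongest reply is that little is lost. The listings and change-from-baseline summaries cover the whole Safety population, whatever the baseline. SAP V.F calls for listings of all recorded data. Marked worsening should also reach the AE tables with a grade: an AE includes exacerbation of a pre-existing condition (Protocol 9.1), a treatment-emergent event includes one that worsens (SAP VIII.C), and the worst grade per patient is used. The Safety Review Committee also sees all Grade 2 or higher toxicity data (Protocol 9.7).

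Most of this stands, and it rules out several stronger readings:
- A reader might infer that such worsening is invisible. It is not; it is missing from one summary.
- A reader might infer that large changes go uncounted, such as hemoglobin from 9.5 to 6.5 g/dL or ALT from 2 to 15 × ULN. Both would very probably become graded AEs. The ALT value fails the dosing-day limit. So does the hemoglobin value unless the patient is transfused, and a transfusion is itself an intervention.
- A reader might infer that the SAP breaks a protocol promise of a graded table. Protocol 10.2 promises grading. The laboratory displays it names are listings and tables of absolute values and changes from baseline. The final output list is also deferred to a shells document that is not available here.

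What the reply does not supply is a count of patients who worsened, by grade and dose, that does not depend on the AE judgement. The DLT definition (Protocol 4.2.4, item 4) also exempts some laboratory abnormalities judged nonsignificant, treatable or reversible, so a Grade 3 or 4 value need not be counted there.

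**Conclusion.** The point holds as a limit of the categorical laboratory summary. For any test on which a patient starts abnormal, the VIII.H shift table cannot register worsening. The SAP has no laboratory grading rule or graded summary to match the grading statement in Protocol 10.2, and its first-value rule is not built to capture the worst value.

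The size is uncertain. The 2 to 12 patients in 20, per test, rest entirely on the assumed 10% to 60% share; only the eligibility limits show that the share can exceed zero. What escapes every graded display is mainly worsening that was not judged clinically significant, led to no dosing action or intervention, and was not recorded at Investigator discretion. It would be wrong to conclude that the dose-finding result is compromised: DLTs are assessed by the Investigator and do not use this table. The change is worth making because it alters the reported safety counts by dose and needs no new data.

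**What to change.** For CTCAE-gradable laboratory tests, replace the normal-to-abnormal table in SAP VIII.H with a table of baseline CTCAE grade against worst post-baseline grade, by arm and dose.

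- Include rows for abnormal and for missing baselines.
- Use all scheduled and unscheduled post-baseline values, and exempt this table from the first-non-missing rule in V.F.
- State in VIII.D how laboratory values are graded under version 5.0, including when the baseline is already abnormal, so that the SAP matches Protocol 10.2.
- Add the table to Appendix 5, which at present lists no shift table.

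The data are already collected, so the cost is SAP text and programming. No visit, sample or protocol procedure changes.

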Study Period	Protocol Section	Screening	Cycle 1							Cycles 2-4	Additional Cycles ¹	EOT/Early Termination Visit	Safety Follow-up Visit	
			1		Dose	(6 ± 1 hours postdose)	2 (24 ± 2 hours postdose)	3 (48 ± 2 hours postdose)	8 ± 1 day	15 ± 1 day	1 ± 1 day			
Study Day	7	-28 to 0		Baseline (predose)										
		7	-28 to 0											
Informed consent/enrollment	7.1	●												
Medical history	7.2.1	●												
Physical examination	7.2.4	●	●			●		●	●	●	●	●	●	●
Height	7.2.4	●												
Weight	7.2.4	●	●			●				●	●	●	●	●
Vital signs (blood pressure, body temperature, pulse, and pulse oximetry) ²	7.2.3	●	●		●	●		●	●	●	●	●	●	●
Screening for hepatitis B, C and HIV	7.2.5	●												
ECGs	7.2.6	●												
MUGA/ECHO	7.2.7	●												
Hematology (CBC with differential)	7.2.5.1	●	●					●	●	●	●	●	●	
Blood chemistry, including LFTs	7.2.5.1	●	●					●	●	●	●	●	●	
Coagulation (PT/aPTT)	7.2.5.1	●	●					●	●	●	●	●	●	
Thyroid function (FT4, TSH)	7.2.5.1	●								● ³	● ³	●		
Urinalysis	7.2.5.1	●												
Cytokine blood draw	7.2.5.2		●		●	●	●	● ⁴	● ⁴	● ⁴	● ⁴	● ⁴	●	
Blood preservation tube for exploratory analyses	7.2.5.2		●					● ⁵		● ^{5,6}				
Kinetics of SYNB1891 (qPCR blood assay)	7.4		●		●	●								
Serum hCG (women of childbearing potential)	7.2.5	●												
Urine hCG (women of childbearing potential)	7.2.5		●							●	●	●		
Telephone call	7.2.2						●							

Study Period	Protocol Section	Screening	Cycle 1						Cycles 2-4	Additional Cycles ¹	EOT/Early Termination Visit	Safety Follow-up Visit	
Study Day	7	-28 to 0	1			2 (24 ± 2 hours postdose)	3 (48 ± 2 hours postdose)	8 ± 1 day	15 ± 1 day	1 ± 1 day	1 ± 1 day	Within 14 days after last dose	30 ± 5 days after last dose
			Baseline (predose)	Dose	(6 ± 1 hours postdose)								
Fine needle aspirate of eligible lesion pre-injection	7.4		● ⁷					● ⁵					
Biopsy of eligible lesion	7.4		● ⁷							● ⁸		● ⁹	
Biopsy of noninjected lesion (if applicable)	7.4		● ⁷							● ⁸		● ⁹	
Administration of SYNB1891 intratumorally	4.2			● ³				● ³	● ³	● ³	● ³		
Tumor response using appropriate imaging	7.3	● ⁴								● ¹⁰	● ¹⁰	● ⁴	
Adverse event reporting	7.2.2		Continuously from the time of informed consent through the Safety Follow-up visit										
Monitoring for symptoms and signs of infection	7.2.2.1		Continuously from the time of informed consent through the Safety Follow-up visit										

Abbreviations: aPTT = activated partial thromboplastin time; CBC = complete blood count; ECG = electrocardiogram; ECHO = echocardiogram; EOT = end of treatment; FT4 = free thyroxine; hCG = human chorionic gonadotropin; HIV = human immunodeficiency virus; LFT = liver function test; MUGA = multi-gated acquisition; qPCR = quantitative polymerase chain reaction; PT = prothrombin time; TSH = thyroid stimulating hormone

¹ Patients who do not have progressive disease (i.e., those who achieve and sustain a complete/partial response or stable disease) may receive additional cycles of SYNB1891 given on Day 1 of each cycle for up to 24 months (i.e., Cycles 5 to 35) after the initial dose of study treatment until documentation of progressive disease or other discontinuation criteria, satisfaction of a predefined stopping rule, or no eligible lesions remain.

² Collected while patients are in a seated or supine position at screening, on Cycle 1 Day 1 (predose and 30 minutes, 1 hour, 2 hours, 3 hours, 6 hours, and 24 hours postdose), on all other study treatment days (predose and 30 minutes, 1 hour, 2 hours, 3 hours, and 6 hours postdose), at EOT/Early Termination and Safety Follow-up, and as clinically indicated.

³ Day 1 of odd-numbered cycles only.

⁴ Predose and 6 hours postdose (as indicated) after every SYNB1891 injection.

⁵ Predose.

⁶ Day 1 of Cycle 3 only.

⁷ The predose (baseline) biopsies and fine needle aspirate may be performed up to 7 days prior to Cycle 1 Day 1.

⁸ Core biopsies will be collected predose on Day 1 of Cycle 2 only (i.e., not Day 1 of Cycles 3 or 4).

⁹ For patients who withdraw from the study prior to Cycle 2 Day 1, the second biopsy should be performed at the EOT visit.

¹⁰ At the end of even-numbered cycles only.

Arm 2:

Study Period	Protocol Section	Screening	Cycle 1							Cycles 2-4	Additional Cycles ¹	EOT/Early Termination Visit	Safety Follow-up Visit				
			1		2 (24 ± 2 hours postdose)	3 (48 ± 2 hours postdose)	8 ± 1 day	15 ± 1 day	1 ± 1 day								
Study Day	7	-28 to 0	Baseline (predose)	Dose													
Informed consent/enrollment	7.1	●															
Medical history	7.2.1	●															
Physical examination	7.2.4	●	●			●		●	●	●	●	●	●				
Height	7.2.4	●															
Weight	7.2.4	●	●						●	●	●	●	●				
Vital signs (blood pressure, body temperature, pulse, and pulse oximetry) ²	7.2.3	●	●		●	●		●	●	●	●	●	●				
Screening for hepatitis B, C and HIV	7.2.5	●															
ECGs	7.2.6	●															
MUGA/ECHO	7.2.7	●															
Hematology (CBC with differential)	7.2.5.1	●	●					●	●	●	●	●	●				
Blood chemistry, including LFTs	7.2.5.1	●	●					●	●	●	●	●	●				
Coagulation (PT/aPTT)	7.2.5.1	●	●					●	●	●	●	●	●				
Thyroid function (FT4, TSH)	7.2.5.1	●							● ³	● ³	●						
Urinalysis	7.2.5.1	●															
Cytokine blood draw	7.2.5.2		●		●	●		● ⁴	● ⁴	● ⁴	● ⁴	● ⁴	●				
Blood preservation tube for exploratory analyses	7.2.5.2			●				● ⁵		● ^{5,6}							
Kinetics of SYNB1891 (qPCR blood assay)	7.4		●		●	●											
Serum hCG (women of childbearing potential)	7.2.5	●															
Urine hCG (women of childbearing potential)	7.2.5		●						●	●	●						
Telephone call	7.2.2						●										
Fine needle aspirate of eligible lesion pre-injection	7.4			● ⁷				● ⁵									

Study Period	Protocol Section	Screening	Cycle 1							Cycles 2-4	Additional Cycles ¹	EOT/Early Termination Visit	Safety Follow-up Visit
Study Day	7	-28 to 0	1			2 (24 ± 2 hours postdose)	3 (48 ± 2 hours postdose)	8 ± 1 day	15 ± 1 day	1 ± 1 day	1 ± 1 day	Within 14 days after last dose	30 ± 5 days after last dose
			Baseline (predose)	Dose	(6 ± 1 hours postdose)								
Biopsy of eligible lesion	7.4		● ⁷							● 8		● ⁹	
Biopsy of noninjected lesion (if applicable)	7.4		● ⁷							● 8		● ⁹	
Administration of SYNB1891 intratumorally	4.2			●					●	●	●		
Administration of atezolizumab by IV infusion	4.2			●						●	●		
Tumor response using appropriate imaging	7.3	●								● ¹⁰	● ¹⁰	●	
Adverse event reporting	7.2.2		Continuously from the time of informed consent through the Safety Follow-up visit										
Monitoring for symptoms and signs of infection	7.2.2.1		Continuously from the time of informed consent through the Safety Follow-up visit										

Abbreviations: aPTT = activated partial thromboplastin time; CBC = complete blood count; ECG = electrocardiogram; ECHO = echocardiogram; EOT = end of treatment; FT4 = free thyroxine; hCG = human chorionic gonadotropin; HIV = human immunodeficiency virus; IV = intravenous; LFT = liver function test;

MUGA = multi-gated acquisition; qPCR = quantitative polymerase chain reaction; PT = prothrombin time; TSH = thyroid stimulating hormone

¹ Patients who do not have progressive disease (i.e., those who achieve and sustain a complete/partial response or stable disease) at the end of Cycle 4 on combination therapy may receive additional cycles of study treatment for up to 24 months (i.e., Cycles 5 to 35) after the initial dose of study treatment until documentation of progressive disease or other discontinuation criteria, satisfaction of a predefined stopping rule, or no eligible lesions remain.

² Collected while patients are in a seated or supine position at screening, on Cycle 1 Day 1 (predose and 30 minutes, 1 hour, 2 hours, 3 hours, 6 hours, and 24 hours postdose), on all other study treatment days (predose and 30 minutes, 1 hour, 2 hours, 3 hours, and 6 hours postdose), at EOT/Early Termination and Safety Follow-up, and as clinically indicated.

³ Day 1 of odd-numbered cycles only.

⁴ Predose and 6 hours postdose (as indicated) after every SYNB1891 injection.

⁵ Predose.

⁶ Day 1 of Cycle 3 only.

⁷ The predose (baseline) biopsies and fine needle aspirate may be performed up to 7 days prior to Cycle 1 Day 1.

⁸ Core biopsies will be collected predose on Day 1 of Cycle 2 only (i.e., not Day 1 of Cycles 3 or 4).

⁹ For patients who withdraw from the study prior to Cycle 2 Day 1, the second biopsy should be performed at the EOT visit.

¹⁰ At the end of even-numbered cycles only.

XIV. Appendix 4: Local and Central Laboratory Parameters

Local Laboratory Parameters

Panel	Parameters	
Hematology	Must be Reviewed Predose:	
	Calculated absolute neutrophil count White blood cell Red blood cell Red cell indices Hemoglobin Hematocrit Platelet count	Neutrophils Lymphocytes Monocytes Eosinophils Basophils
Chemistry	Must be Reviewed Predose:	
	Calcium Chloride Total protein Potassium Glucose Sodium Blood urea nitrogen Creatinine Bicarbonate Albumin Uric acid Phosphorus Magnesium	Alkaline phosphatase Aspartate aminotransferase Alanine aminotransferase Lactate dehydrogenase Direct bilirubin Indirect bilirubin Total bilirubin
Thyroid Function	Must be Reviewed Predose:	
	Free T4	Thyroid-stimulating hormone
Coagulation	May be Reviewed Postdose:	
	Prothrombin time and/or activated partial thromboplastin time International normalized ratio	
Urinalysis	May be Reviewed Postdose:	
	Dipstick: pH Glucose Protein Bilirubin Ketones Leukocytes Blood	Microscopic (if dipstick is positive): White blood cell count Red blood cell count Casts

Central Laboratory Parameters

Panel	Parameters
Cytokines	IL1RA, CXCL10, IFN γ , CXCL5, IL1a, IL6, CCL5, CCL20, TNF α , CCL4, CCL2, S100A8/9 (individual or both), CCL3
qPCR	
• Tumor tissue quantitative polymerase chain reaction (qPCR) from fine needle aspirate• Whole blood qPCR• Whole blood qPCR from blood cultures
NanoString	
• Tumor biopsy samples
Other	Blood samples collected for exploratory analyses in preservation tubes

XV. Appendix 5: Summary Tables, Listing and Figures

The following titles describe planned summary tables, listings, and figures. The final version of this list and additional details can be found in the separate Table, Listings and Figures shells document for Interim Analysis and Final Analysis. Tables may be combined or divided, and title details may be modified during development, if spacing and appearance require doing so.

Additional summary tables may be produced if warranted by collected data. If a table in this appendix is not produced because it is not needed or it would not be informative (as, for example, when two analysis populations converge), that change in the set of data displays will be updated in the TLF shells document.

As a general comment for the tables, all tables will show Arm 1 and Arm 2, separately.

	Table Title	Analysis Population	Interim Analysis (1 st at the end of Arm 1 Cohort 4 [C4]; 2 nd at the end of Arm 1 [E1]; or both [X])
1	Patient Disposition, Number (%) of Patients	Safety	X
2	Demographic and Baseline Characteristics	Safety	X
3	Subject Medical History, Number (%) of Patients	Safety	E1
4	Disease History, Number (%) of Patients	Safety	E1
5	Prior Anti-Cancer Systemic Therapy, Number (%) of Patients	Safety	X
6	Prior Anti-Cancer Radiotherapy Therapy, Number (%) of Patients	Safety	
7	Concomitant Medications, Number (%) of Patients	Safety	
8	Concomitant Procedure, Number (%) of Patients	Safety	
9	Exposure to Study Drug	Safety	X
10	Patients with Dose Modifications or Interruptions	Safety	E1
11	Summary of Tumor Response by RECIST 1.1/iRECIST	Efficacy	X
12	Summary of Lymphoma Response by LYRIC	Efficacy	X
13	Summary of Sum of Diameters of Target Lesion	Efficacy	E1
14	Summary of Injected Lesion	Efficacy	X
15	Summary of Time to Progression by RECIST 1.1	Efficacy	E1
16	Summary of Time to Progression by LYRIC	Efficacy	E1
17	Summary of Progression Free Survival by RECIST 1.1	Efficacy	E1
18	Summary of Progression Free Survival by LYRIC	Efficacy	E1
19	Summary of Duration of Response by RECIST 1.1	Efficacy	

20	Summary of Duration of Response by LYRIC	Efficacy	
21	Dose Limiting Toxicity (DLT), Number (%) of Patients	Safety	X
22	Overall Summary of Treatment Emergent Adverse Events (TEAE), Number (%) of Patients	Safety	X
23	Incidence of Treatment Emergent Adverse Events by Primary MedDRA System Organ Class and Preferred Term, Number (%) of Patients	Safety	E1
24	Incidence of Treatment Emergent Adverse Events by System Organ Class and Preferred Term – Related to SYNB1891, Number (%) of Patients	Safety	E1
25	Incidence of Treatment Emergent Adverse Events by System Organ Class and Preferred Term – Related to Atezolizumab, Number (%) of Patients	Safety	
26	Incidence of Serious Treatment Emergent Adverse Events by System Organ Class and Preferred Term, Number (%) of Patients	Safety	E1
27	Incidence of Serious Treatment Emergent Adverse Events by System Organ Class and Preferred Term – Related to SYNB1891, Number (%) of Patients	Safety	E1
28	Incidence of Serious Treatment Emergent Adverse Events by System Organ Class and Preferred Term – Related to Atezolizumab, Number (%) of Patients	Safety	
29	Incidence of Grade 3 or Greater Treatment Emergent Adverse Events by System Organ Class and Preferred Term, Number (%) of Patients	Safety	E1
30	Incidence of Grade 3 or Greater Treatment Emergent Adverse Events by System Organ Class and Preferred Term – Related to SYNB1891, Number (%) of Patients	Safety	E1
31	Incidence of Grade 3 or Greater Treatment Emergent Adverse Events by System Organ Class and Preferred Term – Related to Atezolizumab, Number (%) of Patients	Safety	
32	Incidence of Treatment Emergent Adverse Events Leading to Any Study Drug Discontinuation by System Organ Class and Preferred Term, Number (%) of Patients	Safety	
33	Incidence of Treatment Emergent Adverse Events Leading to SYNB1891 Discontinuation by System Organ Class and Preferred Term, Number (%) of Patients	Safety	
34	Incidence of Treatment Emergent Adverse Events Leading to Atezolizumab Discontinuation by System Organ Class and Preferred Term, Number (%) of Patients	Safety	

35	Incidence of Treatment Emergent Adverse Events Resulting in SYNB1891 Dose Interruption by System Organ Class and Preferred Term, Number (%) of Patients	Safety	
36	Incidence of Treatment Emergent Adverse Events Resulting in Atezolizumab Dose Interruption by System Organ Class and Preferred Term, Number (%) of Patients	Safety	
37	Incidence of Treatment Emergent Adverse Events Resulting in SYNB1891 Dose Modification by System Organ Class and Preferred Term, Number (%) of Patients	Safety	
38	Incidence of Treatment Emergent Adverse Events Resulting in Atezolizumab Dose Modification by System Organ Class and Preferred Term, Number (%) of Patients	Safety	
39	Incidence of Treatment Emergent Adverse Events Resulting in Death by System Organ Class and Preferred Term, Number (%) of Patients	Safety	
40	Incidence of Treatment Emergent Adverse Events of Special Interest by System Organ Class and Preferred Term, Number (%) of Patients	Safety	E1
41	Incidence of Treatment Emergent Adverse Events by System Organ Class, Preferred Term and Maximum Severity, Number (%) of Patients	Safety	E1
42	Incidence of Treatment Emergent Adverse Events by System Organ Class, Preferred Term and Action Taken, Number (%) of Patients	Safety	
43	Incidence of Treatment Emergent Adverse Events by Preferred Term, Number (%) of Patients	Safety	
44	Mean Change in Clinical Chemistry Parameters Over Time	Safety	
45	Mean Change in Hematology and Coagulation Parameters Over Time	Safety	
46	Mean Change in Thyroid Function Parameters Over Time	Safety	
47	Mean Change in Vital Signs Over Time	Safety	
48	Mean Change in Pharmacodynamic Over Time	PK/PD	
49	Mean Change in Pharmacokinetics Over Time	PK/PD	

	Listing Title	Analysis Population	Interim Analysis (1st at the end of Arm 1 Cohort 4 [C4]; 2nd at the end of Arm 1 [E1]; or both [X])	Comment
1	Patient Disposition	Safety	X	
2	Screening and Enrollment Status	Safety	X	
3	Protocol Deviations	Safety	X	
4	Demographic Characteristics	Safety		
5	Subject Medical History	Safety		
6	Disease History	Safety	X	
7	Prior Anti-Cancer Systemic Therapy	Safety	X	
8	Prior Anti-Cancer Radiotherapy	Safety		
9	Prior/Concomitant Medications	Safety		
10	Prior/Concomitant Procedures	Safety		
11	Intratumoral Administration of SYNB1891	Safety	X	
12	Administration of Atezolizumab by IV Infusion	Safety		
13	Dosing Compliance/Exposure	Safety		
14	Core Biopsy of Lesion	Safety		
15	RECIST 1.1 Target Lesions	Safety	E1	
16	RECIST 1.1 Non-Target Lesions	Safety	E1	
17	RECIST 1.1 New Lesions	Safety	E1	
18	RECIST 1.1 Injected Lesions	Safety	E1	
19	RECIST 1.1 Response Assessment	Safety	X	19.1. iRECIST
20	LYRIC Target Lesions	Safety	E1	
21	LYRIC Non-Target Lesions	Safety	E1	
22	LYRIC New Lesions	Safety	E1	
23	LYRIC Injected Lesions	Safety	E1	
24	LYRIC Response Assessment	Safety	X	
25	Adverse Events	Safety	X	
26	Serious Adverse Events	Safety	X	
27	Adverse Events of Special Interest	Safety		
28	Adverse Events Leading to Any Study Drug Discontinuation	Safety	X	
29	Adverse Events Leading to Death	Safety	X	

30	Clinical Chemistry	Safety	X	
31	Hematology and Coagulation	Safety	X	
32	Thyroid Function Tests	Safety		
33	Vital Signs	Safety	X	
34	Physical Examination	Safety		
35	12-Lead ECG	Safety		
36	Multi-gated Acquisition Scan or Echocardiogram	Safety		
37	Urinalysis	Safety		
38	Pregnancy Test	Safety		
39	Virology (Hepatitis B, C, and HIV)	Safety		
40	Pharmacodynamic	PK/PD		
41	Pharmacokinetics	PK/PD		
42	Core Biopsies	Safety		
43	Unscheduled Assessment	Safety		

As a general comment on the figures, all figures will combine RECIST and LYRIC.

	Figures Title	Analysis Population	Interim Analysis (1st at the end of Arm 1 Cohort 4 [C4]; 2nd at the end of Arm 1 [E1]; or both [X])
1	Waterfall Plot of Change in Tumor Size from Baseline to Patients' Best Tumor Response at Any Time Point	Efficacy	X
2	Waterfall Plot of Change in Tumor Size from Baseline to Patients' Best Tumor Response at Any Time Point Comparing Injected and Non-injected Lesions	Efficacy	X
3	Waterfall Plot of Change in Tumor Size from Baseline to Patients' Best Tumor Response at Any Time Point for Injected Lesions	Efficacy	X
4	Spaghetti Plot of Tumor Response	Efficacy	X
5	Swimmer Plot of Tumor Response	Efficacy	X
6	PK Linear and Semi-log Graph	PK/PD	(Optional)
